 - a. Phone assessment for any new or ongoing symptoms performed by one of the physicians, research nurse or study coordinator
Prednisone decreased to 5mg if no new symptoms
 - b. Schedule urgent visit if new or worsening symptoms
10. Study visit 6 – eight weeks after first study visit
 - a. Patient assessed for partial disease remission defined as:
 - i. no new disease manifestations
 - ii. no worsening of existing disease
 - iii. BVAS/WG < 3
 - b. Adverse events assessed by one of the investigators

- c. Prednisone discontinued (or reduced to patient's stable chronic dose of prednisone in order to avoid adrenal insufficiency) if patient meets partial disease remission criteria Omeprazole discontinued
 - d. Laboratory tests – CBC, CMP, ESR, CRP, ANCA, urinalysis, B-cell flow cytometry
11. Phone call – nine weeks after first study visit
- a. Phone assessment for any new or ongoing symptoms performed by one of the physicians, research nurse or study coordinator Laboratory tests – CBC, CMP, ESR, CRP
 - b. Schedule urgent visit if new/worsening symptoms or worsening laboratories
12. Study visit 7– twelve weeks after first study visit
- a. Focused history and physical exam performed by one of the investigators
 - b. BVAS/WG assessed by one of the investigators
 - c. Adverse events assessed by one of the investigators
 - d. Laboratory tests – CBC, CMP, ESR, CRP, ANCA, urinalysis
13. Phone call – sixteen weeks after first study visit
- a. Phone assessment for any new or ongoing symptoms performed by one of the investigators
 - b. Laboratory tests – CBC, CMP, ESR, CRP, ANCA, and urinalysis
 - c. Schedule urgent visit if new/worsening symptoms or worsening laboratories
14. Study visit 8 – twenty weeks after first study visit
- a. Focused history and physical exam performed by one of the investigators
 - b. BVAS/WG assessed by one of the investigators
 - c. Adverse events assessed by one of the investigators
 - d. Laboratory tests – CBC, CMP, ESR, CRP, ANCA, urinalysis
15. Study visit 9 – twenty-four weeks after first study visit
- a. Focused history and physical exam performed by one of the investigators
 - b. BVAS/WG and VDI assessed by one of the investigators
 - c. Primary outcome measured - defined as BVAS/WG = 0 and prednisone dose = 0 (or maintained at patient's stable chronic dose of prednisone in order to avoid adrenal insufficiency) with no preceding flares.
 - d. Adverse events assessed by one of the investigators

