- Second limited flare - treatment according to best medical judgment of the investigator.

Severe flares – BVAS/WG ≥ 3 or experiencing one of the major BVAS/WG items.

- Patients with severe flares will be treated according to best medical judgment of the investigator.

Termination of protocol

The following pre-defined events will lead to subject's treatment according to best medical judgment:

- Two limited flares - defined as having a new occurrence or worsening of one or more minor BVAS/WG items.
- One severe flare - defined as BVAS/WG ≥ 3 or experiencing one of the major BVAS/WG items)
- Failing to achieve disease response at 4 weeks following the first rituximab infusion - defined as no new disease manifestations, no worsening of existing disease and stable or improved BVAS/WG score
- Failing to achieve partial remission at 8 weeks following the first rituximab infusion - defined as no new disease manifestations, no worsening of existing disease and BVAS/WG < 3 .

Subjects treated according to best medical judgment will continue to be followed according to a modified visit schedule of no less than once every three months for 12 months from study entry.

Data Collection

Data, including BVAS/WG scores, blood and urine test results, relevant radiology and pathology findings will be kept on data collection sheets and on Partners workstations or encrypted mobile devices using unique patient identifiers. Drs. [name], [name], [name], [name] as well as [name], [name], [name] and study staff will have access to coding sheets linking patient names and their unique identifiers. The data collection sheets will be kept in a locked file cabinet in the Rheumatology Unit.

Drs. [name] and [name] will review data on the number of subjects having limited or severe flares, achieving disease response, achieving partial remission and achieving remission after the first ten patients have been followed for six months. [name] will be responsible for determining whether the research should be altered or stopped.

PI's intention is to maintain the subject files electronically through utilizing a Redcap database as well as accessing additional information from LMR. The current Redcap

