- Grade 3 = Severe and undesirable adverse event
- Grade 4 = Life-threatening or disabling adverse event
- Grade 5 = Death

VI. Statistical Analysis

The following variables will be collected during the study:

- Baseline variables
 - o Age
 - o Sex
 - o Disease type (GPA or MPA)
 - o ANCA type
 - o New or relapsing disease
 - o If relapsing disease - treatment prior to flare
 - o BVAS/WG
 - o VDI
- BVAS/WG at visits 1 and 5-11
- VDI at visits 9 and 11
- Laboratory data at baseline and at visits 3, 5, 6, 7, 8, 9, 10 and 11 and after phone calls at 6,9 and 16 weeks of the study
 - o CBC
 - o CMP
 - o ESR
 - o CRP
 - o ANCA
 - o Urinalysis
 - o Flow cytometry for B-cells (measured at visits 1, 5, 9, 10, 11)
 - o HACA (measured at visits 1, 9, 11)
 - o Quantitative immunoglobulins (measured at visits 1, 9 and 11)
 - o Mechanistic studies (optional) (visit 1, 9, 11)
- Prednisone dose at each visit
- Adverse events

Study endpoints

Primary endpoint (assessed at 24 weeks) - Number of patients entering remission defined as BVAS/WG = 0 and prednisone dose = 0 (or maintained at patient's stable chronic dose of prednisone in order to avoid adrenal insufficiency).

Secondary endpoints (assessed at 24 weeks)

- Number of early treatment failures defined as patients who have new or worsening disease manifestations assessed at 4 weeks after study entry
- Number of severe flares defined as flare with BVAS/WG ≥ 3 or experiencing one of the major BVAS/WG items
- Number of limited flares defined as having a new occurrence or worsening of one or more minor BVAS/WG items
- Number of patients having a disease response
- Number of patients entering partial remission
- Number of patients entering sustained remission defined as BVAS/WG = 0, prednisone dose = 0 (or maintained at patient's stable chronic dose of prednisone in order to avoid adrenal insufficiency) and no disease flares during the study period.
- Area under the curve BVAS/WG

- Total GC dose

Statistical Methods

Continuous data will be summarized using descriptive statistics (e.g., mean, standard deviation, median, minimum, and maximum). Categorical data will be assessed using the Chi-square and the Fisher exact tests as appropriate. Descriptive statistics and two-sided 95% confidence intervals will be calculated to assist in the interpretation of efficacy outcomes.

Power Analysis

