- Infections are a concern with all drugs that affect the immune system. Rituximab has been associated with reactivation of hepatitis B virus and progressive multifocal leukoencephalopathy infection, in addition to other common viral and bacterial pathogens. Rituximab may decrease immunoglobulin levels. In the event of a severe infection immunoglobulins will be checked in order to determine whether the administration of intravenous immunoglobulin is indicated.
- Skin reactions, painful sores, ulcers, blisters and peeling skin (rare).
- Decreased white blood cell counts.

We anticipate that the risk of many of the infections which patients treated with the combination of rituximab and GCs are prone to will be attenuated by the shorter GC courses prescribed in this protocol.

There may be other risks of rituximab that are currently unknown.

VIII. Potential Benefits

Benefits to participating individuals

Individual patients may benefit from effective control of their disease with decreased toxicity from GC therapy.

Benefits to society

Results of this study may elucidate the optimal dose of GCs in the treatment of severe autoimmune disease such as AAV. Decreasing administration of GCs may decrease their side effects and thus decrease the cost burden on society associated with treatment of severe autoimmune disease.

IX. Monitoring and Quality Assurance

Drs. [name] and [name] will monitor study data to ensure the safety of patients. A formal compilation of safety and efficacy data will be performed after ten patients have been enrolled in the study and followed for six months.

Specific elements related to the safety of study subjects that will be examined include:

- Deaths
- Flares
- Failure to achieve disease response, partial remission or remission.
- Hospitalizations from any cause
- Infections
- Infusion reactions
- Status of peripheral B cell pool with regard to reconstitution
- Other unexpected and serious adverse events

Specific elements of efficacy that will be examined include:

- Decrease in disease activity as assessed by the BVAS/WG score
- Ability to discontinue GCs

The study will be terminated if 60% of subjects fail the primary endpoint. This includes patients who have one severe flare, two limited flares or discontinue the study medication due to an adverse event.

Adverse event reporting guidelines:

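### Follow-up after leaving protocol treatment fixes no week-24 assessment, and Section VI gives no denominator or off-protocol rule for the 24-week endpoints

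*Combined protocol and SAP*

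**What the plan says.** Section V.A, Termination of protocol, begins "The following pre-defined events will lead to subject's treatment according to best medical judgment". It lists two limited flares, one severe flare, no disease response at week 4 and, in the plan's words, "Failing to achieve partial remission at 8 weeks following the first rituximab infusion". Patients who meet any of these "continue to be followed according to a modified visit schedule of no less than once every three months for 12 months from study entry". No visit is tied to week 24, and no assessments are listed for the modified visits.

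Section VI, Study endpoints, states: "Primary endpoint (assessed at 24 weeks) - Number of patients entering remission defined as BVAS/WG = 0 and prednisone dose = 0", with an allowance for patients on a stable chronic dose. The secondary endpoints are also headed as assessed at 24 weeks. They include flare counts, BVAS/WG area under the curve and total glucocorticoid (GC) dose. Section VI names no analysis set, denominator or missing-data rule.

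Two other places bear on the primary endpoint. Study visit 9 in Section V.A gives the same definition but adds "with no preceding flares". Section IX, describing failure of the primary endpoint for the stopping rule, says: "This includes patients who have one severe flare, two limited flares or discontinue the study medication due to an adverse event". It does not name patients who leave at week 4 or week 8.

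**The concern.** The patients who leave protocol treatment are those in whom the short GC course did worst. They are also the only patients whose follow-up is no longer tied to the time at which the endpoints are read. A site could comply fully with the three-monthly rule and still hold no BVAS/WG or prednisone record near week 24 for them.

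The endpoints that need values through week 24 suffer most: BVAS/WG area under the curve, total GC dose, and flares after the one that led to exit. Incomplete data here fall on the patients likely to have most of each, so the regimen could look more GC-sparing and better controlled than it was. GC sparing is the rationale for the study.

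The primary endpoint is exposed in a narrower way. Section VI is where the analysis is defined, and it neither treats leaving protocol treatment as failure nor says how many patients the count is taken over. In a single-arm study of 20, each patient is worth 5 percentage points (1/20).

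**Working it through.** **1. The plan's own figure.** The sample size of 20 (Section VI, Power Analysis) is a convenience sample based on one year's expected enrolment. There is no formula behind it, so there is nothing to reproduce.

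**2. Calendar check.** Inputs: primary assessment at week 24 (Study visit 9); a 10-day rescheduling window (Missed visits); a longest gap of three months. Three months = 365.25/12 × 3/7 = 13.04 weeks. The window is 24 ± 10/7, that is weeks 22.57 to 25.43. The assumption is that visits fall at the longest permitted gap, counted from exit.

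| Exit week | Next visits (weeks) | Visit nearest week 24 | In window? |
|---|---|---|---|
| 4 | 17.0, 30.1 | 42.6 days late | No |
| 8 | 21.0, 34.1 | 20.7 days early | No |
| 12 | 25.0, 38.1 | 7.3 days late | Yes |
| 16 | 29.0, 42.1 | 35.3 days late | No |
| 20 | 33.0, 46.1 | exit visit itself, 28 days early | No |

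Exits between weeks 22.57 − 13.04 = 9.53 and 25.43 − 13.04 = 12.38 give a later visit inside the window. An exit visit from week 22.57 onward is itself inside it. Weeks 4 and 8, the two fixed decision points, are in neither range.

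Under the other natural reading, visits at months 3, 6, 9 and 12 from entry, month 6 is 2 × 13.04 = 26.09 weeks. That is 14.6 days after week 24 on a strict calendar, or on time if six months is read as week 24, as the protocol often does. The text does not require this calendar.

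**3. BVAS/WG area under the curve.** Section VI schedules BVAS/WG at Visits 1 and 5 to 11. Up to week 24 that is weeks 0, 4, 8, 12, 20 and 24: six points. At the longest gap, and if BVAS/WG is scored at the modified visits, a week-4 exit has weeks 0, 4 and 17 (three of the six), and its last value is 24 − 17.0 = 7.0 weeks short. A week-8 exit has weeks 0, 4, 8 and 21 (four), and is 24 − 21.0 = 3.0 weeks short.

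**4. Primary endpoint, definitions side by side.**

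| Event before week 24 | Study visit 9 | Section IX | Section VI |
|---|---|---|---|
| One severe flare | Failure | Failure, named | Depends on week-24 values |
| Two limited flares | Failure | Failure, named | Depends on week-24 values |
| No week-4 response | Failure if it is a flare | Not named | Depends on week-24 values |
| No week-8 partial remission | Failure if it is a flare | Not named | Depends on week-24 values |
| One limited flare (stays on protocol) | Failure | Not named; two are listed | Depends on week-24 values |

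Under Section VI alone, a patient who had a severe flare, was re-treated, and had BVAS/WG 0 off prednisone at week 24 would count as a remission.

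**5. Illustration of the denominator.** Let x be remissions and d failures left out. The reported rate is x/(20 − d), and the inflation is x·d / [20(20 − d)]. Both x and d are assumptions.

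| x | d = 0 | d = 2 | d = 4 |
|---|---|---|---|
| 8 | 40.0% | 44.4% | 50.0% |
| 10 | 50.0% | 55.6% | 62.5% |
| 12 | 60.0% | 66.7% | 75.0% |
| 14 | 70.0% | 77.8% | 87.5% |

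For x = 12 the exact (Clopper-Pearson) 95% intervals are 36.1–80.9% for 12/20, 41.0–86.7% for 12/18 and 47.6–92.7% for 12/16.

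**The case against.** The strongest reply is that the primary endpoint hardly needs week-24 data in these patients. Study visit 9 excludes anyone with an earlier flare, and Section IX names severe and repeated limited flares as failures. That stands for flare exits under those two sections.

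The reply can be pressed further. Failing at week 4 means new or worse disease or a higher score, and failing at week 8 can mean BVAS/WG of 3 or more, which is literally the severe-flare threshold. So most of these exits may be flares too. This narrows the gap but does not close it. Entry itself requires BVAS/WG of at least 3, and a stable score counts as response at week 4, so the threshold cannot sensibly make every persistently active patient a flare. Nor does the reply touch Section VI, which has no flare condition.

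A reader might infer more than the documents support:

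- **That failures are removed from the denominator.** No text removes anyone; the plan is silent. The 75% against 60% contrast rests on assumed inputs.
- **That almost any exit date misses week 24.** This holds only for the longest gap counted from exit. Three-monthly is a minimum frequency, and a month 3/6/9/12 calendar comes close.
- **That the week-4 and week-8 counts are lost.** Each is assessed at or before the exit it triggers. A week-4 exit may have no Visit 6, but this matters only for the unstated denominator of partial remission.
- **That damage scores are a lost endpoint.** VDI is collected but is not a listed endpoint.
- **That GC dose and flares vanish.** The triggering flare is known, prednisone dose is to be collected at each visit, and clinical notes are a data source. The risk is incompleteness between widely spaced visits.

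**Conclusion.** The point holds in limited form. The modified schedule guarantees neither a week-24 visit nor its content, and patients leaving at week 4 or week 8 can miss the 10-day window by about 11 days or more (20.7 − 10 = 10.7 days for week 8; 42.6 − 10 = 32.6 days for week 4). This rests on the longest permitted gap counted from exit.

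The main exposure is BVAS/WG area under the curve, total GC dose and later flares to week 24. The primary endpoint is settled as failure for flare exits by Study visit 9 and Section IX. It remains open for week-4 and week-8 exits that do not meet a flare definition, and for every exit under the Section VI wording.

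The possible effect on the remission rate, 7 to 15 percentage points for an assumed 12 of 20 with two or four failures left out, shows what an unstated denominator permits. It is not an estimate of bias. For a descriptive pilot this is a gap to correct, not a reason to distrust the design.

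**What to change.** 1. **Section V.A, Termination of protocol.** Keep Visit 9 (week 24) and Visit 11 (month 12) for every subject, with their BVAS/WG, VDI, prednisone, adverse-event and laboratory items, and place the quarterly visits around them. At each modified-schedule visit record BVAS/WG and prednisone dose, including dose changes since the last visit. Retaining Visit 9 alone would not restore the area under the curve or the total dose.
2. **Section VI.** State that the denominator is all patients who received the first rituximab infusion, and that a missing week-24 assessment counts as not in remission.
3. **Study visit 9, Section VI and Section IX.** Reconcile the primary-endpoint definition so that a patient who met any of the four off-protocol criteria before week 24 cannot count as a primary remission. State how a single limited flare is classified. Without this step, keeping Visit 9 could turn a flared and re-treated patient into a success under Section VI.

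The cost is a few sentences and some constraint on when the quarterly visits fall; a patient leaving shortly before week 24 may be seen sooner than the minimum frequency requires. The stated remission rate may be slightly less favourable. No treatment decision changes.

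### The primary endpoint is stated inconsistently: one limited flare fails a patient at Visit 9, does not in Section VI, and is not listed in the Section IX stopping rule

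*Combined protocol and SAP*

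**What the plan says.** **Section VI, Study endpoints:** "Primary endpoint (assessed at 24 weeks) - Number of patients entering remission defined as BVAS/WG = 0 and prednisone dose = 0", with the stable chronic dose as the alternative. There is no flare condition. One appears instead in a secondary endpoint: "Number of patients entering sustained remission defined as BVAS/WG = 0, prednisone dose = 0" (or chronic dose), plus freedom from flares over the study. That item sits under a heading that begins "Secondary endpoints (assessed at 24 weeks", yet Section V.A, Study visit 11, assesses sustained remission at 12 months.

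**Section V.A, Study visit 9 (24 weeks):** the primary outcome has the same BVAS/WG and prednisone criteria, but its wording finishes "in order to avoid adrenal insufficiency) with no preceding flares".

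**Section IX:** "The study will be terminated if 60% of subjects fail the primary endpoint". It continues: "This includes patients who have one severe flare, two limited flares or discontinue the study medication due to an adverse event".

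**Section V, Treatment of flares and Termination of protocol:** a first limited flare is treated within the protocol. Protocol treatment ends at one severe flare or at the second limited flare: "Two limited flares - defined as having a new occurrence or worsening of one or more minor BVAS/WG items". Patients who leave protocol treatment are followed on a "modified visit schedule of no less than once every three months for 12 months from study entry".

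**The concern.** The aim in Section II is both to induce remission and to keep it to six months. The Section VI endpoint is status at one time point. It credits a patient who flared, was re-treated and was back in remission off prednisone at week 24; the Visit 9 endpoint does not. The Section VI rate can therefore only equal or exceed the Visit 9 rate.

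The missing clause is unlikely to be shorthand. A few lines later Section VI adds freedom from flares to sustained remission, so within that section the flare condition is what separates the secondary from the primary.

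Two things depend on the answer: the headline proportion of an uncontrolled 20-patient pilot, and a termination rule that refers to the primary endpoint by name. If the definition is left open, it could be chosen after the outcomes are known.

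**Working it through.** The plan gives no assumed remission rate and no power calculation, so there is no figure of its own to reproduce. The check compares the definitions and then illustrates the consequence.

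**1. Classification.** Take patients who have BVAS/WG = 0 and prednisone 0 (or chronic dose) at week 24:

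| History before week 24 | Visit 9 | Section VI | Section IX |
|---|---|---|---|
| One limited flare | Fail | Success | Not listed |
| Two limited flares, or one severe flare | Fail | Success | Fail |
| No flare, but discontinued for an adverse event | Success | Success | Fail |

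No two columns agree throughout.

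**2. Can the first row occur?** The course for a first limited flare is 1 week plus a 4-week taper, 5 weeks in all. Since 24 − 5 = 19, a full course begun by about week 19 can end by week 24. The cut-off is approximate, because the taper may be shortened and visits may move by 10 days.

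**3. Headline rate.** n = 20 (Section VI, Power Analysis), so one patient is 1/20 = 5 points. The plan asks for two-sided 95% intervals. The exact (Clopper-Pearson) limits for x successes are the 2.5% quantile of Beta(x, n − x + 1) and the 97.5% quantile of Beta(x + 1, n − x). Assume 14 successes under Section VI, of whom 0 to 3 had flared earlier:

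| Earlier flares among the 14 | Visit 9 result | Exact 95% CI |
|---|---|---|
| 0 (same as Section VI) | 14/20 = 70% | 45.7–88.1% |
| 1 | 13/20 = 65% | 40.8–84.6% |
| 2 | 12/20 = 60% | 36.1–80.9% |
| 3 | 11/20 = 55% | 31.5–76.9% |

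**4. Stopping rule.** Severe flares and two limited flares are already listed as failures, so the open flare group is one limited flare followed by remission. Let p be the share failing for any other reason (assumed 20%, 30% or 40%) and s the share in the open group (assumed 5% or 10%). Section IX does not say when the 60% is applied. Assume first that it means at least 6 of 10 at the ten-patient review. The chance of stopping is P(X ≥ 6), with X ~ Bin(10, p) if the group is not counted and X ~ Bin(10, p + s) if it is:

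| p | Not counted | Counted, s = 5% | Counted, s = 10% |
|---|---|---|---|
| 20% | 0.6% | 2.0% | 4.7% |
| 30% | 4.7% | 9.5% | 16.6% |
| 40% | 16.6% | 26.2% | 37.7% |

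If it means at least 12 of 20, then with p = 30% the chance is 0.5% when the group is not counted, against 2.0% (s = 5%) or 5.7% (s = 10%) when it is.

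**The case against.** **Two definitions, not three.** Section IX introduces its list as inclusions. The list cannot be complete, since it omits a patient who simply has active disease or is still on prednisone at week 24. Silence on a single limited flare is therefore weak evidence of a separate rule. This stands as far as it goes: such a patient is not listed, which is not the same as a success. But the items that are listed still conflict with Section VI (a recovered severe flare) and with both definitions (a flare-free remitter who discontinued for an adverse event).

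**Few patients are affected.** New or worsening disease at the week-4 or week-8 assessment ends protocol treatment, so single limited flares handled purely by the protocol course fall mainly between about weeks 8 and 19. Rituximab ends at week 3 and prednisone at week 8, so few can discontinue for an adverse event. Both points are fair and limit the likely number. At 5 points per patient, a small number still matters.

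**Both rates will be reported anyway.** They will if sustained remission is read at 24 weeks, as its heading says. What then remains is which rate is primary, and the plan does not say. If it is read at 12 months, as at Visit 11, Section VI has no flare-free rate at week 24.

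**The ten-patient review sees flares separately, and a named individual decides on stopping.** That reduces the risk of an unnoticed misapplication. It does not define what counts toward the 60%.

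**This is a descriptive pilot, and the illustrated intervals overlap heavily.** That is true, and there is no formal test to invalidate. The estimate and its interval are then the main efficacy result, so they need a single meaning.

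**Conclusion.** The concern holds. Two explicit definitions of the primary endpoint disagree about any patient who flares and then remits by week 24, and the failure list in the stopping rule matches neither. The conflict rests on the text alone. Its size depends on how many such patients occur, which the documents do not let one estimate: 5 points on the headline rate for each patient. Under the assumed rates above, counting single limited flares raises the chance of stopping at ten patients by about 1 to 21 points. The importance of the finding does not rest on those probabilities. It rests on a headline result and a termination rule that both use an endpoint without one fixed meaning. It must be corrected.

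**What to change.** 1. Use one definition of the primary endpoint in Visit 9, Section VI and Section IX. The aim in Section II supports the Visit 9 version: BVAS/WG = 0 and prednisone 0 (or stable chronic dose) at week 24, with no earlier limited or severe flare.
2. State once, for both the analysis and the stopping rule, how a single limited flare, a severe flare and discontinuation for an adverse event each count.
3. State when the 60% is applied, and have the sponsor confirm that threshold against the chosen definition.
4. If the Visit 9 version is adopted, report week-24 status regardless of flares as a secondary endpoint, and name the visit that supplies it for patients on the modified schedule.
5. Place sustained remission at 12 months, in line with Visit 11, so that it does not duplicate the primary.

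Item 1 is the essential correction, with items 2 and 3 needed to make the stopping rule usable; items 4 and 5 tidy up what follows from it.

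**Cost.** Amendment wording; the primary needs no new data. The reported remission rate may be lower and the stopping rule may be met more often. The added secondary needs a named week-24 assessment, because the modified schedule guarantees only one visit every three months.
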